4.3.1. Withdrawal for Worsening Asthma

Patients who meet the alert criteria and/or who experience a clinically meaningful worsening of their asthma will be assessed by the investigator. If the investigator considers it is not possible to safely manage a patient in a blinded manner as patient's asthma warrants a change in his/her asthma treatment, the IMP will be stopped, and appropriate treatment (based on the investigator's judgment) should be offered. The medical monitor should be contacted to confirm the findings when alternative therapy is to be instituted. The patient should continue in the study until the patient has completed all remaining study visits and the FV.

- For the purpose of this study, an asthma exacerbation is defined as worsening of asthma requiring any significant treatment other than IMP and study rescue medication. Significant treatment includes the use of systemic corticosteroids and/or the addition of other ICS-containing asthma medications, LABAs, or other NCS asthma medications, for example, inhaled short-acting muscarinic antagonist; ER/urgent care clinic visit; or hospitalization. Note: A single dose of nebulized albuterol/salbutamol would not meet the criteria for an asthma exacerbation. ER/urgent care clinic visits where the treatment is limited to a single dose of nebulized albuterol/salbutamol will not meet the criteria of an asthma exacerbation.

4.3.2. Alert Criteria for Worsening Asthma

Alert criteria for individual patients with worsening asthma have been designed to ensure patient safety. If any of the criteria listed below are met, during scheduled or unplanned study visit, the investigator will determine whether the patient's overall clinical picture is consistent with worsening asthma and if the patient should be withdrawn from IMP (but not the study) to be placed on alternative asthma therapy in the interest of patient safety. In cases where the IMP is to be withdrawn and alternative therapy started, the investigational center staff should contact the medical monitor to confirm the findings. Meeting 1 of these alert criteria does not automatically require a patient to be withdrawn from IMP, rather it requires a clinical evaluation to determine if the patient's asthma can continue to be managed in a blinded manner per the study or necessitates a change in asthma therapy. All attempts will be made to safely continue to manage a patient in a blinded manner.

- Morning FEV₁ by handheld device measured at home falls below the FEV₁ stability limit (see Section 6.1.3) calculated at the SV for the run-in period and at baseline for the treatment period on 4 or more days (do not have to be consecutive) out of any 7-day period (7-day period is defined as any consecutive 7 days following the RV and can overlap with scheduled study investigational center visits).

- Based upon a review of patient data from the patient diary built into the handheld device, the patient has experienced any of the following during a 7-day period (7-day period is defined as any consecutive 7 days following a previous TV; 7 days can overlap with scheduled study investigational center visits):
 - 3 or more days in which 8 or more inhalations/day of rescue medication (albuterol/salbutamol HFA MDI [90 mcg ex-actuator] or equivalent) were used (any 3 days in the consecutive 7-day period)
 - 3 or more days in which the patient experienced a nighttime asthma symptom score of more than 2 (any 3 days in the consecutive 7-day period)

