- ^g Daily morning and evening lung function assessments (FEV₁ and PEF) by handheld device (after the patient is trained on its use and has demonstrated proper technique using the provided training device) will be performed, except as indicated. The patient will be instructed to perform 3 trough morning FEV₁ maneuvers and 3 evening FEV₁ maneuvers at home each day during participation in the run-in period and the treatment period (morning only on the final TV [TV6 (week 12)]). The highest FEV₁ obtained at the SV will be used to calculate the home FEV₁ stability limit, which will be used for review of alert criteria during the run-in period. The average FEV₁ over 5 days prior to RV will be used to calculate the alert criteria for the treatment period.
- ^h 60-minute (± 10 minutes) postdose lung function assessments will be performed at the investigational center at all visits (excluding patients placed on alternative therapy where the patient will not dose but a 1-hour assessment will still be collected).
- ⁱ Except patients who have been placed on alternative therapy.
- ^j Rescue medication will be dispensed for all patients entering the run-in period. At each visit, the study personnel should determine if the patient has adequate rescue medication remaining (based on current use) or dispense a new albuterol/salbutamol HFA MDI. A second inhaler may be provided for use at school or camp, as applicable. Rescue medication dispensed at SV will be used for response to a bronchodilator test.
- ^k The investigational center staff must verify that the information from the patient diary built into the handheld device is up to date and identify any potential missing data or deviations upon review of the patient diary built into the handheld device at that visit. The device will be collected and inspected to make sure it is not damaged and the data will be downloaded at each clinic visit. Once inspected, the same handheld device will be redispensed to the patient unless it needs to be replaced.
- ^l The investigator will discuss ongoing asthma treatment with the patient after lung function assessments have been completed, and any medication started for the purpose of ongoing asthma treatment will not be considered a protocol violation. This treatment, if instituted, should be entered in the CRF as ongoing therapy.

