Patients meeting all of the inclusion criteria and none of the exclusion criteria at the SV will begin a 14- to 30-day run-in period. Albuterol/salbutamol hydrofluoroalkane (HFA) metered-dose inhaler (MDI; a SABA inhaler) will be provided to replace the patient's current rescue medication, and is to be used as needed for symptomatic relief of asthma symptoms during the run-in and treatment periods, with a maximum of 12 inhalations permitted per day.

Starting day 1 of the run-in period, patients must discontinue their current ICS or ICS/LABA therapy and all other nonstudy asthma-related drugs and instead take a patient-blinded MDPI placebo device (1 inhalation twice daily).

The intent of the run-in period is to complete baseline safety evaluations, establish patient compliance, and obtain baseline measures of asthma symptoms, rescue use, and lung function assessment values. Patients (with assistance from parents/legal guardians/caregivers, as needed) will record symptoms, rescue use, and lung function assessments (FEV₁ and PEF) in the patient diary built into the handheld device throughout the 14- to 30-day run-in period to establish their baseline profiles. Patients and parents/legal guardians/caregivers will be instructed to contact their investigator if they have met predefined asthma alert criteria.

14. Procedures Before Investigational Medicinal Product Treatment (Baseline [Randomization Visit (RV)/TV1])

Patients who meet the inclusion and exclusion criteria at visit SV will continue to RV/TV1. At the RV/TV1, patient will be assessed for randomization. Patients who meet all of the randomization criteria will be randomized into the double-blind treatment period of the study. Note: response to bronchodilator testing may not be conducted on the same day as the randomization visit.

The following procedures will be performed at the RV/TV1:

- review randomization criteria
- inquire about adverse events and concomitant medications
- perform vital signs measurements

- perform directed cardiopulmonary examination
- perform oropharyngeal examination
- perform urine pregnancy test (for females of childbearing potential, as applicable)
- perform predose lung function assessments (FEV₁ and PEF) by handheld device
- provide training on IMP and have patient demonstrate proper technique using the provided training device before dosing with IMP. The training inhaler is to be kept at the clinic and not provided to the patient to keep at home.
- dispense IMP

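### The FEV1 alert criterion sets a run-in limit but counts only 7-day windows after the RV, and the two diary windows are unclear for the run-in

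*Protocol*

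**What the plan says.** Protocol Section 4.3.2 lists three alert criteria; the synopsis and Section 3.1 repeat them with the same windows.

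- **FEV1.** The home morning value is compared with a stability limit that is "calculated at the SV for the run-in period and at baseline for the treatment period". The criterion is met when the value is below the limit "on 4 or more days (do not have to be consecutive) out of any 7-day period". The window is then defined: "7-day period is defined as any consecutive 7 days following the RV".
- **Rescue use and nighttime symptom score.** Both share one window definition: "7-day period is defined as any consecutive 7 days following a previous TV".

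Other places put alert review in the run-in. Section 6.1.3 calculates a limit at the SV and assigns it to the run-in. Table 3 footnote g says that the home limit derived from the SV is one "which will be used for review of alert criteria during the run-in period". Appendix B Part 13, which describes the run-in, says that patients and families "will be instructed to contact their investigator if they have met predefined asthma alert criteria". Table 3 and Appendix B Part 14 both schedule an alert-criteria assessment at RV/TV1.

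**The concern.** The first half of the FEV1 criterion provides a limit for the run-in, and the second half removes every window in which that limit could be applied. A center or device programmer who follows the window definition would never evaluate the criterion before randomization. One who follows footnote g or Section 6.1.3 would.

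This matters because in the run-in every child has stopped asthma medication and is taking placebo. Section 1.3.2 defends the use of placebo partly on the ground that device and diary alerts will catch deterioration early, and it cites Section 4.3.2 for this. The trial has also seen unclear FEV1-window wording cause errors. Letter of Clarification 02 reports that an ambiguous 7-day eligibility rule was programmed wrongly, and that some patients were randomized without meeting it. The documents do not say how the alert windows were programmed or how centers read them.

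**Working it through.** No sample size, power or alpha figure is involved. The check is a comparison of definitions plus one count.

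**Inputs**
- Run-in: from SV to RV, 14 to 30 days (Section 3.1).
- The RV is TV1 and ends the run-in (Section 3.1).
- FEV1 window: 7 consecutive days after the RV (Section 4.3.2).
- Diary windows: 7 consecutive days after a previous TV (Section 4.3.2).

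**Count of windows**, assuming one home morning reading on each run-in day. A period of *d* days contains *d* − 7 + 1 consecutive 7-day windows.
- Shortest run-in: 14 − 7 + 1 = 8.
- Longest run-in: 30 − 7 + 1 = 24.
- Of these 8 to 24 windows, the number that follow the RV is 0, because the RV comes after all of them.

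The FEV1 criterion therefore has no window in which the SV-based limit can be used. This follows from Section 4.3.2 alone, and it contradicts Section 6.1.3 and footnote g.

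**Diary criteria.** The result depends on what counts as a TV.
- Section 6.2.1 lists the TVs from the RV onward. On that reading, no TV precedes any run-in day and the count is again 0.
- Section 6.2.3 counts the SV among the visits called TVs. On that reading, run-in windows after the SV would qualify.

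No passage gives either diary criterion an explicit run-in version. The link to the run-in is the general instruction in Appendix B Part 13. The diary windows are therefore unclear for the run-in, whereas the FEV1 window is contradictory.

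**RV/TV1 assessment.** On the day of the RV no 7-day window after the RV has yet elapsed. An alert assessment on that day can only look back over run-in data, which the FEV1 window definition does not admit. This scheduled procedure is a further item that does not fit the definition.

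**The case against.** The strongest reply is that this is a slip in a parenthesis. Footnote g, Section 6.1.3 and Appendix B Part 13 all point to alert review in the run-in, and a sensible reader would apply the SV limit there. Meeting a criterion only calls for a clinical evaluation. Sections 3.1 and 4.3.1 already call for one when asthma worsens, whether or not a criterion is met. No child has been identified who would go unassessed.

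Much of that stands, and it rules out four stronger conclusions that a reader might draw.

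- *No alert of any kind can occur in the run-in.* Section 6.1.3 describes an on-screen device alert whenever a value falls below the limit, with no 7-day window attached.
- *All three criteria are shut out of the run-in.* That is firm only for FEV1. For the two diary criteria the documents leave the meaning of TV open.
- *Table 3 confirms the exclusion because its alert row starts at the RV.* The row points the other way, since an assessment on the RV day can only review run-in data. The device and diary are first handed out at the SV, so there are no home data to review at that visit.
- *Run-in safety monitoring rests on these criteria.* The documents also provide investigator assessment of worsening asthma (Sections 3.1 and 4.3.1), the device alert, unscheduled visits (Appendix B Part 17), and a randomization criterion of no run-in exacerbation (Section 5.9).

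What the reply does not remove is the contradiction. The same wording stands in three places, and the protocol does not say which passage governs.

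**Conclusion.** The FEV1 alert criterion contradicts itself. As written it cannot be met in the run-in: 0 of the 8 to 24 possible 7-day windows qualify, although two other passages say that the SV limit is used there. The diary windows are ambiguous for the same period.

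The first part rests only on the RV being the end of the run-in, which Section 3.1 states. The second rests on the conflict between Sections 6.2.1 and 6.2.3 over which visits are TVs.

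The wording applies to every child who enters the run-in, for up to 30 days each. That measures who is exposed to the unclear rule, not how many would be harmed, and the documents give no basis for the latter. This is an internal inconsistency in a safety rule, with other safeguards still in place. It should be corrected, but it does not show that the run-in is unmonitored. A correction helps only children still to enter the run-in. Section 9.1 reports 434 patients past week 12 when the sample size was revised, so at most 824 − 434 = 390 remained to be randomized at that point, plus any run-in failures.

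**What to change.** Reconcile the window definitions in the synopsis, Section 3.1 and Section 4.3.2 with Section 6.1.3, Table 3 footnote g, Appendix B Part 13, and the RV/TV1 alert assessment in Table 3 and Appendix B Part 14. For each of the three criteria, state whether the 7-day window covers the run-in, the treatment period or both. Use one definition of TV in Sections 4.3.2, 6.2.1 and 6.2.3. Confirm that the device programming and center instructions match the reconciled text. Which period each criterion should cover is for the sponsor to decide; no threshold or management rule is proposed here.

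The cost is small: wording in a letter of clarification or the next amendment, a route the sponsor has already used for Table 3 and for FEV1-window wording, plus a check of the alert programming.

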4.4. Replacement of Patients

A patient who is randomized but does not complete the treatment period will not be replaced.

4.5. Rescreening

Patients who have not met inclusion criteria for response to a bronchodilator and cannot return within 7 days for a retest should be classified as screen failures but may be rescreened. Patients who experience an URI or LRI during the run-in period should be classified as randomization failures and be discontinued from the study, but may be rescreened 2 weeks after resolution of the infection. Patients who are rescreened will need to repeat all screening procedures and evaluations. Only 1 retest and 1 rescreening for each patient will be permitted.

The decision to retest or rescreen patients will be based on the investigator's judgment and the study protocol. In cases of rescreening, the sponsor or designee should be notified of the pending rescreening. Patients may retest/rescreen for lung function assessments and response to a bronchodilator only if they meet all other nonspirometric inclusion/exclusion criteria. At the retest, patients will be asked if they have had any adverse events, changes in medications, or changes in medical history. Patients will not be eligible to enter the run-in period until all inclusion/exclusion criteria are met.

4.6. Screening Failure

Screening failures are defined as participants who consent to participate in the clinical study but do not subsequently enter the placebo run-in period. Minimal information includes but is not limited to demography, screening failure details, eligibility criteria, and any serious adverse events.

Randomization failures are defined as participants who enter the placebo run-in period but are not subsequently randomized (ie, do not meet the randomization criteria).

5. TREATMENTS

5.1. Investigational Medicinal Products Used in the Study

IMP is defined as the test IMPs, reference IMPs, and matching placebo IMPs to the respective test and reference IMPs. Details for each IMP are provided below and in [Table 4](#). (Note: The use of spacers or chambers for inhalers is not permitted with IMP inhalers [test or placebo] or rescue inhalers.)

5.1.1. Test Investigational Medicinal Product

The investigation products include the following:

- **Treatment A:** Fp MDPI 25 mcg, 1 inhalation twice daily
- **Treatment B:** Fp MDPI 50 mcg, 1 inhalation twice daily
- **Treatment C:** FS MDPI 50/12.5 mcg, 1 inhalation twice daily

5.1.2. Placebo Investigational Medicinal Product

The placebo used in this study includes the following:

- **Treatment D:** Placebo MDPI 0 mcg, 1 inhalation twice daily

Table 4: Investigational Medicinal Products Used in the Study

IMP Name	Fp MDPI	FS MDPI	Placebo IMP
Trade name and INN, if applicable, or company-assigned number	Fluticasone Propionate Inhalation Powder	Fluticasone Propionate/Salmeterol Inhalation Powder	Placebo inhalation powder
Formulation	Inhalation powder	Inhalation powder	Inhalation powder
Unit dose strength(s)/Dosage level(s)	25 mcg or 50 mcg	50/12.5 mcg	0 mcg
Route of administration	Inhalation	Inhalation	Inhalation
Dosing instructions	1 inhalation twice daily approximately 12 hours apart	1 inhalation twice daily approximately 12 hours apart	1 inhalation twice daily approximately 12 hours apart
Packaging	Inhaler device	Inhaler device	Inhaler device
Manufacturer	[REDACTED]	[REDACTED]	[REDACTED]

Fp=fluticasone propionate; FS=fluticasone propionate/salmeterol; IMP=investigational medicinal product; INN=international nonproprietary name; MDPI=multidose dry powder inhaler.

5.2. Preparation, Handling, Labeling, Storage, and Accountability for Investigational Medicinal Products

5.2.1. Storage and Security

For the purposes of the study, test IMPs (Fp MDPI, FS MDPI) and placebo with Teva MDPI devices must be stored between 15° and 25°C (59° and 77°F) in a dry place away from direct heat and sunlight, and in a securely locked, substantially constructed cabinet or enclosure. All rescue medication (albuterol/salbutamol HFA) will be stored according to the manufacturer's drug product stipulation, in a dry place, and in a securely locked, substantially constructed cabinet or enclosure. Maintenance of a daily temperature log (manual or automated) is required.

Each IMP shipment will include a packing slip listing the contents of the shipment and a device for monitoring and recording temperatures. The investigator is responsible for ensuring that deliveries of IMP and other study materials from the sponsor are treated as follows:

- correctly received and recorded
- handled and stored safely and properly in accordance with the Code of Federal Regulations (CFR) or local regulations
- used in accordance with this protocol

The investigational center personnel are responsible for the acknowledgement of the receipt using the interactive response technology (IRT).

Detailed instructions regarding labeling (eg, investigational centers indicating the use by date) of the IMP are provided in the study operations manual.

5.2.2. Labeling

Supplies of IMPs will be labeled according to the current International Council for Harmonisation (ICH) guidelines on Good Clinical Practice (GCP) and Good Manufacturing Practice and will include any locally required statements. If necessary, labels will be translated into the local language.

5.2.3. Accountability

Each IMP shipment will include a packing slip listing the contents of the shipment, drug return instructions, and any applicable forms.

The investigator is responsible for ensuring that deliveries of IMP and other study materials from the sponsor are correctly received, recorded, handled, and stored safely and properly in accordance with the CFR or national and local regulations, and used in accordance with this protocol.

The IMP for this study must be used in accordance with the protocol and may be dispensed to patients only by authorized study investigational center personnel. The investigator is responsible for drug accountability, reconciliation, and record maintenance. In accordance with applicable regulatory requirements, the investigator or designated study investigational center personnel must maintain IMP accountability records.

A record of IMP accountability (ie, IMP and other materials received, used, retained, returned, or destroyed) should be documented in the IRT and signed by the principal investigator or designee, with an account given for any discrepancies. Empty, partially used, and unused IMP will be returned to the sponsor or designee.

5.3. Justification for Investigational Medicinal Products

5.3.1. Justification for Dose of Test Investigational Medicinal Product

The Fp MDPI doses to be evaluated in this study (25 mcg twice daily and 50 mcg twice daily) were selected for study in patients 4 through 11 years of age based on the adult dose-ranging study. Based on the results from the adult and adolescent Phase 3 clinical trials (submitted for FDA review in March 2016), the 25- and 50-mcg twice-daily doses were confirmed as reasonable for studies in patients 4 through 11 years of age.

The FS MDPI dose to be evaluated in this study (50/12.5 mcg twice daily) was selected for study in patients 4 through 11 years of age based on the adult and adolescent dose-ranging study, which showed that FS MDPI at a total daily dose of 100/50 mcg was superior to ADVAIR DISKUS in its effects on FEV₁ over the 12 hours after a single dose, while lower doses of FS MDPI were generally comparable.

A detailed description of IMP administration is presented in Section 5.1.

5.3.2. Justification for Use of Placebo Investigational Medicinal Product

A placebo was elected to be used in this study in order to evaluate the efficacy of treatment with Fp MDPI or FS MDPI versus rescue treatment only in patients with persistent asthma.

5.4. Other Medicinal Products/Non-Investigational Medicinal Products

Not applicable.

5.5. Treatment After the End of the Study

No IMP will be provided beyond completion of the study. Patients should return to their primary care physician for treatment after study completion.

